Appendix D. Laboratory Parameters in Conventional Unit

All clinical laboratory parameters will be reported in the International System (SI) units as standard practice. In addition, descriptive statistics for values and changes from baseline in conventional units at all assessed visits will be reported for selected laboratory parameters as listed in the following table.

Table 9. List of Selected Parameters Reported in Conventional Unit

Number	Laboratory Parameter	Conventional Unit	Decimal Places
1	Alanine Aminotransferase (SGPT)	U/L	0
2	Albumin	g/dL	1
3	Alkaline Phosphatase	U/L	0
4	Aspartate Aminotransferase (SGOT)	U/L	0
5	Bilirubin, Direct (Conjugated)	mg/dL	1
6	Bilirubin, Indirect (Unconjugated)	mg/dL	1
7	Bilirubin, Total	mg/dL	1
8	Blood Urea Nitrogen	mg/dL	0
9	Calcium	mg/dL	1
10	Cholesterol, HDL	mg/dL	0
11	Cholesterol, LDL	mg/dL	0
12	Cholesterol, LDL direct and calculated (combined) (This lab parameter could be the same as #11)	mg/dL	0
13	Cholesterol, Total	mg/dL	0
14	Creatine Kinase	U/L	0
15	Creatinine	mg/dL	1
16	Glucose	mg/dL	0
17	Insulin	µIU/mL	1
18	Triglycerides	mg/dL	0
19	Uric Acid	mg/dL	1
20	Hemoglobin	g/dL	1

Patient narratives will also include the values in conventional units for the selected lab parameters in below table. That will be accomplished by presenting the values in conventional units within the parentheses next to the values in SI units.

Table 10. Presenting Laboratory Data Using SI and Conventional Units in Narratives

LABORATORY DATA						
Lab Test	Test Name	Normal Range		VISIT01	VISIT05	VISIT07
		Low	High	2012-07-03	2012-08-07	2012-09-04
CHEMISTRY	Bilirubin, Total ($\mu\text{mol/L}$ (mg/dL))	0 (0)	18.81 (1.1)	6.84 (0.4)	5.13 (0.3)	5.13 (0.3)

Appendix E. List of Abbreviations

Abbreviation/Term	Definition
AE	adverse event
ALP	alkaline phosphatase
ALT	alanine aminotransferase
AST	aspartate aminotransferase
C-SSRS	Columbia–Suicide Severity Rating Scale
DSMB	Data Safety Monitoring Board
eCRF	electronic case report form
ECG	electrocardiogram, electrocardiographic
EM	episodic migraine
EOS	end of study
ET	early termination
IWRS	interactive web response system
LLN	lower limit of normal value
LSM	least squares mean
MedDRA	Medication Dictionary for Regulatory Activities
mITT	modified intent-to-treat
MMRM	mixed-effects model for repeated measures
PCS	potentially clinically significant
PT	preferred term
Q1	first quartile (25th percentile of the data)
Q3	third quartile (75th percentile of the data)
QD	once daily
QTc	QT interval corrected for heart rate
QTcB	QT interval corrected for heart rate using the Bazett formula ($QTcB = QT/(RR)^{1/2}$)
QTcF	QT interval corrected for heart rate using the Fridericia formula ($QTcF = QT/(RR)^{2/3}$)
SAE	serious adverse event
SAP	statistical analysis plan
SI	Le Système International d'Unités (International System of Units)
SOC	standard of care
TBL	total bilirubin
TEAE	treatment-emergent adverse event
ULN	upper limit of normal value
WHO	World Health Organization

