APPENDIX A. STUDY-SPECIFIC ABBREVIATIONS AND TERMS

Abbreviation	Definition
AE	Adverse event
AESI	Adverse events of special interest
ALT	Alanine aminotransferase
AST	Aspartate aminotransferase
CL/F	Apparent clearance
CBD	Cannabidiol
CGRP	Calcitonin gene-related peptide
COVID-19	Coronavirus Disease – 2019
CRP	C-reactive protein
C-SSRS	Columbia-Suicide Severity Rating Scale
DMC	Data Monitoring Committee
eCRF	Electronic case report form
ECG	Electrocardiogram
EDC	Electronic data capture
EM	Episodic Migraine
FDA	Food and Drug Administration
GCP	Good Clinical Practice
HEAC	Hepatic Event Adjudication Committee
HIT-6	Headache Impact Test-6
ICHD	International Classification of Headache Disorders
INR	International normalized ratio
IRT	Interactive response technology
IV	Intravenous
mITT	Modified intent-to-treat
MSQ v2.1	Migraine-Specific Quality of Life Questionnaire version 2.1
MTOQ-6	Migraine Treatment Optimization Questionnaire-6
NSAID	Non-steroidal anti-inflammatory drug
PCR	Polymerase chain reaction
PGIC	Patient Global Impression of Change
PHQ-4	Patient Health Questionnaire-4
PK	Pharmacokinetic(s)

QTcF	QT interval corrected for heart rate using Fridericia's formula
SAE	Serious adverse event
SAP	Statistical analysis plan
SNRI	Serotonin-norepinephrine reuptake Inhibitor
SSRI	Selective serotonin reuptake inhibitor
SUSAR	Suspected unexpected serious adverse reactions
THC	Tetrahydrocannabinol
ULN	Upper limit of normal
US	United States
V/F	Apparent volume of distribution
WPAI:MIGRAINE	Work Productivity and Activity Impairment Questionnaire: Migraine

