10.5 Other Safety Analyses

10.5.1 Electrocardiogram

Descriptive statistics for ECG parameters (i.e., heart rate, PR interval, QRS interval, RR interval, QT interval, and QTc interval) at baseline, postbaseline, and changes from baseline values at each postbaseline timepoint will be presented for the Safety Populations 1 and 2.

ECG parameter values are considered PCS if ECG values meet either the actual value or change from baseline PCS high criteria listed in Table 7. The number and percentage of subjects with PCS postbaseline values will be summarized. The percentages will be calculated relative to the number of subjects with an available non-PCS baseline value and at least 1 postbaseline assessment. The numerator will be the total number of subjects with an available non-PCS baseline value and at least 1 PCS postbaseline ECG value during the study. A supportive listing of subjects with PCS postbaseline values will be provided. A listing of all AEs for participants with PCS ECG values will also be provided.

The number and percentage of subjects meeting each of the criteria for postbaseline ECG values of clinical interest listed in Table 5 will be summarized. Subjects will be counted only once for the most severe category. A supportive listing of participants with postbaseline QTcF increases > 30 msec will be provided, including the PID number, study center, and all QTc values (including changes from baseline). A listing of all AEs for participants with postbaseline QTcF increases > 30 msec will also be provided.

A shift table from baseline to the end of open-label treatment period in the investigator's overall interpretation of the ECG will be presented for the following categories: normal; abnormal, not clinically significant; abnormal, clinically significant. A tabular display of subjects with postbaseline clinically significant ECG abnormalities according to the investigator's overall interpretation will be provided.

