SBP = Systolic blood pressure; DBP = Diastolic blood pressure; bpm = beats per minute

ECG parameter values are considered PCS if ECG values meet either the actual value or change from baseline PCS high criteria listed in the following table.

Table 7. Potentially Clinically Significant Criteria for ECG Parameters

Parameter	Unit	Criterion
QRS interval	msec	≥ 150
PR interval	msec	≥ 250
QTc (QTcB or QTcF) interval	msec	> 500
QTc (QTcB or QTcF) interval	msec	Increase from baseline > 60

Table 8. ECG Post-baseline Values of Clinical Interest

Parameter	Unit	Criterion
QTcF interval	msec	> 450
		> 480
		> 500
		Increase > 30 but ≤ 60
		Increase > 60

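### SAP Table 7 pools QTcB with QTcF in one PCS flag; once QTcF is computed with the cube root, most QTc flags arising without a drug effect could be Bazett-only

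*SAP*

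**What the plan says.** - **SAP Appendix C, Table 7** sets the QTc criteria on "QTc (QTcB or QTcF) interval": a value > 500 msec, or an increase from baseline > 60 msec.
- **SAP 10.5.1** makes one criterion enough: "ECG parameter values are considered PCS if ECG values meet either the actual value or change from baseline PCS high criteria". It also fixes the denominator: "The percentages will be calculated relative to the number of subjects with an available non-PCS baseline value and at least 1 postbaseline assessment".
- **SAP Appendix C, Table 8** uses QTcF only, at > 450, > 480 and > 500 msec, "Increase > 30 but ≤ 60", and an increase > 60 msec. The listings in SAP 10.5.1 for increases > 30 msec are also triggered by QTcF. Subjects in the Table 8 summary are counted once, in their most severe category.
- **SAP 10.5.1** also plans descriptive statistics for a QTc interval without saying which correction is meant.
- **SAP Appendix E** defines QTcB as the "QT interval corrected for heart rate using the Bazett formula", with exponent 1/2 on RR. The next line prints QTcF with exponent 2/3.
- **Protocol Appendix A** lists only QTcF: "QT interval corrected for heart rate using Fridericia's formula".
- ECG variables belong to the primary endpoint (SAP 3.1). The protocol has no control group (section 4.2) and schedules ECGs at Visits 1, 5 and 8 (Appendix D).

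**The concern.** The two corrections respond differently to heart rate. If QTcF is the cube-root correction, QTcB rises with heart rate while QTcF stays put. A rule satisfied by either one will therefore pick up subjects whose QTcF is unremarkable but whose heart rate was higher at a postbaseline ECG.

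No control arm would show the same background rate of such flags. A handful of PCS QTc cases among about 235 subjects could be read as an effect on repolarisation. Table 8 uses the same > 500 and > 60 msec limits with a different QTc, so a reader could meet two counts for what looks like one criterion.

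**Working it through.** **Inputs from the documents.** The Table 7 limits (> 500, > +60 msec); Bazett exponent 1/2; printed QTcF exponent 2/3; one baseline and two postbaseline ECGs; 235 subjects, about 200 after 15% dropout (235 × 0.85 = 199.75). **Not in the documents.** The cube root (exponent 1/3) is the definition of the named Fridericia method. All QT and heart-rate variability figures below are assumptions.

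**Step 1: the formulas.** QTc = QT/RR^e with RR = 60/HR. The plan's own printed formulas, for QT 360 msec:

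| HR | cube root (1/3) | Bazett (1/2) | QTcF as printed (2/3) |
|---|---|---|---|
| 90 | 412.1 | 440.9 | 471.7 |
| 100 | 426.8 | 464.8 | 506.1 |

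The printed QTcF lies above QTcB at any heart rate over 60; the cube-root QTcF lies below it.

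**Step 2: QTcB against cube-root QTcF.** QTcB = QTcF × (HR/60)^(1/6). The factor is 1.070 at HR 90 and 1.089 at HR 100.
- QTcB passes 500 once QTcF reaches 500/1.070 = 467 (HR 90) or 500/1.089 = 459 (HR 100).
- With QTcF constant at 420, going from HR 60 to 90 raises QTcB by 420 × 0.0699 = 29.4 msec, and from 60 to 100 by 420 × 0.0889 = 37.3 msec.
- The QTcF rise still needed for QTcB +60 is (60 − 29.4)/1.070 = 28.6 msec, or (60 − 37.3)/1.089 = 20.8 msec.

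**Step 3: heart rate by itself.** From HR 60 with QTcF fixed at 420, QTcB rises > 60 msec only at 60 × (480/420)^6 ≈ 134 bpm, and exceeds 500 only at 60 × (500/420)^6 ≈ 171 bpm.

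**Step 4: simulation, no drug effect, cube-root QTcF.** Assumed: QTcF mean 415 and between-subject SD 17; HR mean 70 and between-subject SD 8; within-subject HR SD 7 to 10. Expected PCS subjects per 235:

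| Within-subject QTcF SD | QTcF only | Either | Bazett-only (difference) |
|---|---|---|---|
| 10 | 0.01 | 0.4 to 1.2 | 0.4 to 1.2 |
| 12 | 0.1 | 1.1 to 2.4 | 1.0 to 2.3 |
| 15 | 1.1 | 3.8 to 6.0 | 2.7 to 4.9 |

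The Bazett-only share is 71% to 99%. With QTcF held constant within subject, so that only heart rate varies, the either-rule flags only about 0.05 to 0.12 subjects per 235.

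**Step 5: a second set of assumptions, per 200 subjects.** QTc mean 405 to 415, between-subject SD 17 to 20, within-subject SD 10 to 20; HR mean 68 to 75, within-subject SD 7 to 12.

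| Scenario | Cube-root QTcF only | QTcB or cube-root QTcF | QTcF as printed | QTcB or QTcF as printed |
|---|---|---|---|---|
| narrow | 0.01 | 0.17 | 4.94 | 4.94 |
| middle | 0.89 | 4.35 | 24.16 | 24.21 |
| wide | 6.67 | 19.35 | 55.05 | 55.35 |

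With the cube root, the Bazett-only share is 66% to 95%. With the printed exponent it is at most 0.6%.

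**The case against.** The case for leaving Table 7 alone has substance.

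- **PCS flags are descriptive screens, and a wide net is defensible.** This stands, but separate QTcB and QTcF rows keep the same sensitivity.
- **QTcF-only counts are already planned.** Table 8 gives them at > 500 and > 60 msec, and heart rate, RR and QT are summarised. This limits the harm. The QTcF > 30 msec listing helps less: in Step 2, a QTcF rise of 28.6 msec suffices for a QTcB rise of 60, and that subject would not enter the listing. The PCS listing would include the subject, but the SAP does not say that it shows both corrections.
- **The numbers are assumed and small.** This stands. Step 4 also gives every subject two postbaseline ECGs despite the 15% dropout; scaled to 200, its range becomes about 0.3 to 4.2.

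A reader might also infer more than the documents support:

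- *That a faster heart rate alone produces most of the flags.* Step 3 and the heart-rate-only result in Step 4 show otherwise. Rate and ordinary QTcF variation act together.
- *That Bazett is the source of false flags in the SAP as printed.* With exponent 2/3, QTcF itself is the source, and in Table 8 too.
- *That the either-rule can only add flags.* A baseline QTcB > 500 removes a subject from the denominator, so a later QTcF flag could be lost. The loss is negligible, about 0.001 to 0.006 subjects per 235.
- *That the SAP contradicts the protocol.* An abbreviation entry is not an analysis specification, and Protocol 7.5 refers only to ECG parameters.

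**Conclusion.** The point holds conditionally, and it is minor. Table 7 does not separate QTcB from QTcF, while Table 8 and the > 30 msec listings use QTcF alone. Once QTcF is the cube-root correction, the pooled rule adds roughly 0.4 to 5 Bazett-only PCS subjects per 235 in the main scenarios. The narrow alternative adds about 0.2 per 200 (0.17 − 0.01), and the widest about 12.7 (19.35 − 6.67). Bazett-only cases are the majority of QTc flags in every cube-root scenario tested, and no comparator is available to show the background rate.

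This rests on two things. The first is the assumed QT and heart-rate variability with no drug effect. The second is the QTcF formula actually used: if the programs follow Appendix E as printed, QTcB changes the count by less than 1%, and the exponent is the larger problem. If the ECG vendor or the programs already use the cube root, the pooling matters now.

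**What to change.** 1. Check the QTcF exponent in the source file of SAP Appendix E and in the vendor or program specification. If 2/3 is what it says, correct it to QTcF = QT/RR^(1/3). This comes first, because dropping QTcB alone would leave the printed formula's flags in both tables.
2. In Table 7, base the QTc PCS flag and the non-PCS-baseline denominator on QTcF. If QTcB is kept, give it its own supportive row that sets neither the flag nor the denominator.
3. In SAP 10.5.1, name QTcF as the QTc interval summarised. In the same edit, change the reference for ECG values of clinical interest from Table 5, which holds the hepatic criteria, to Table 8.

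Tables 7 and 8 will then use the same QTc. Their figures can still differ, because Table 7 requires a non-PCS baseline and the Table 8 summary counts each subject in the most severe category only; a footnote should say so.

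The cost is a few text edits and no new data. The PCS count becomes less comparable with tables that pooled QTcB and QTcF, which the separate QTcB row largely offsets.

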Appendix F. Changes to Protocol-planned Analyses

There are no changes from the protocol-planned analyses.
